## **5.7 NSAIDs and management of joint stiffness and pain with AI use**

Musculoskeletal complaints are among the most commonly reported and debilitating side effects of adjuvant hormonal therapy (SERMs and, particularly, AIs)(Thorne 2007). Among women with chronic arthralgia syndromes at initiation of AI therapy, half report symptom exacerbation. Joint related symptoms manifest early after initiation of AI therapy with peak incidence reported at 6 months.(Howell et al. 2005) While the exact mechanism is unclear, joint and muscle pain in women increases with age, with the maximum increase observed between 50 and 59 years old(Wolfe et al. 1995; Croft et al. 1993). This pattern is consistent with age-related declines in estrogen as a potential causal factor. The incidence of rheumatoid arthritis is also highest in the decade following menopause and has been linked to estrogen deprivation. Increased inflammation mediated by bradykinin and the pro-inflammatory prostaglandins is mechanistically linked to symptoms(Thorne 2007). Thus, NSAIDs are recommended for symptom management and commonly used among patients given access to over-the-counter formulations. This raises the important possibility that findings from observational studies suggesting lower breast cancer recurrence risk among NSAID users may arise as a consequence of improved tolerance to their hormonal therapy and better adherence instead of direct anti-tumor effects of the NSAIDs themselves. The effect of NSAID use on hormonal therapy adherence and pain scores has

not, to our knowledge, been formally investigated in a randomized study. Secondary analysis of patients in the CAAN trial, discussed above, showed that participants who completed the Functional Assessment of Cancer Therapy Core questionnaire (FACT-G) including the breast cancer subscale scores suggested that the participants randomized to exemestane plus celecoxib experienced positive changes in the FACT-B and FACT-G scores following 4-weeks of therapy(L. W. Chow et al. 2008). Improved measures of quality of life were significant in the coxib group when compared to negative changes in the exemestane only group and a third group that received letrozole only therapy. These data support the general thinking that the addition of an NSAID to AI might improve quality of life though effects on pain scores were not investigated as a possible explanation in the CAAN study.

## 5.8 Overall significance of the study

Here we seek to obtain evidence from human studies for two clinically significant questions about the role of NSAIDs in women receiving AIs for their breast cancer. First, we will investigate the effect of AIs on BD, a putative biomarker for future chemoprevention studies and an NSAID on breast tissue as an indicator of drug action in the breast using novel imaging approaches discussed below. Second, we will examine pathways involved in BD and patient reported outcomes (PRO) of bone and joint pains, a frequent cause of patient non-adherence to AI therapy. Also, to ask if prescribed NSAID use at AI initiation reduces pain. Findings from this study will be used in decision making about a larger trial to test the question of whether NSAIDs increase the efficacy of AIs for reducing cancer recurrence by modulating risk features of the breast (*i.e.*, BD, ADC, proliferation and apoptosis biomarkers), by increasing adherence as a consequence of reducing joint and muscle pain, or both.

# 6 OBSERVATION STUDY GROUP

## 6.1 Rationale for Observation Arm

Previous randomized controlled studies have shown that AIs do not decrease BD after 12 months of use in the contralateral breast of breast cancer patients compared to a placebo (see Table 1 above). These studies do, however show the presence of a mean decline in BD related to age of 1-3%.

In healthy, postmenopausal women, the mean age-related change in BD by mammography at 2-yrs has been reported from randomized trials to be -1.3% ( $\pm$  2.9%). These studies were conducted using computer assisted algorithms to estimate BD from mammograms. However, other studies using visual estimation of BD on mammography have reported that as high as 30% of women show greater than a 1-standard deviation in variance with repeated measurement. This high variability is attributable to the visual estimation of BD from mammogram and highlights the need to use methods with lower between-measure variances. In our own analysis of BD estimation using FWMRI, between-measure variability

is on the order of 1-2% with BD estimates highly correlated with those of CAD-derived BD estimates from mammograms (Abstract P6-01-18, Thomson, [name] and Stopeck, SABCS Dec 2014). However, there are no studies that have utilized FWMRI to evaluate change in BD over 12 months for women on AIs. And while the expected change is likely to be comparable to that previously reported using CAD measures of mammograms (-1 to -3%), we will determine change in BD for women on AIs at 6 and 12 months by FWMRI and control for time on AI. Other variables such as starting BD, age and BMI will be considered as important covariates. The primary purpose of this study is to establish the magnitude of BD change as assessed by FWMRI and will be used in interpreting findings of the significance of any change in the sulindac intervention arm component of our study and for planning future interventions targeting BD change in patients on AIs.

## 6.2 Hypothesis and Specific Aims

We hypothesize that AI therapy for 12 months will not change BD on average more than 3%.

### 6.2.1 Primary Aim

Compare change in BD as measured by MRI-acquired fat-to-water ratio (FWR-MRI) in the contralateral, unaffected breast in women receiving AI therapy as part of their standard of care therapy.

### 6.2.2 Secondary Aims

- a) To monitor changes in pain scores using the Brief Pain Inventory-Short form (BPI-SF) during 12 months of AI therapy.
- b) To quantify changes in the apparent diffusion coefficient (ADC) of water measured by diffusion-weighted MRI (DW-MRI) over 12 months in the contralateral, unaffected breast in women receiving AI therapy as part of their standard of care therapy or prevention of breast cancer.

## 7 SULINDAC INTERVENTION STUDY

### 7.1 Rationale for Sulindac Intervention Study

Here, we propose that one approach to advance the indication of NSAID use for 2nd prevention is to combine their use in ER+ patients on AIs. This combination builds on the evidence that favors the anti-tumor action and the efficacy of NSAIDs for the management of muscle/skeletal complaints as an approach to enhance the benefit-to-risk ratio associated with chronic daily NSAID use. Here, we propose novel magnetic resonance imaging (MRI) approaches as a non-invasive and sensitive effect measure of sulindac, a potent, non-selective NSAID, on 'high-risk' breast tissue. In addition and importantly, because sulindac as a prodrug (Clinoril™), has been shown previously in 2 of 3 studies to spare renal synthesis of the vasodilatory prostaglandins in patients with normal renal function (Sedor

et al. 1984; Cibattoni et al. 1987; Roberts et al. 1985; A. G. Johnson 1998), we will conduct a comprehensive analysis of sulindac effect on mean arterial pressure in the chronic daily use setting to better inform on hypertensive risk related to daily sulindac use in women receiving AIs.

## 7.2 Specific Aims and Study Hypotheses for the Sulindac Intervention Arm

To assess the benefit of sulindac in ER+ patient receiving AIs, 100 breast cancer patients, stable on AI therapy for ER+ tumors will receive 12 months of AI + sulindac at 150 mg bid. Study participants will serve as their own controls. To control for the variability in the endpoints, we propose an initial NSAID washout period of 1 month followed by a 3 months' observation (no sulindac) period, at the end of which, we will measure change in BD by MRI between baseline 1 (post NSAID washout) and baseline 2 (no NSAID observation period of 3 months). The change in BD from the baseline MRI to the first follow-up MRI at 3 months on study will provide the baseline BD measurement for our subsequent BD analyses (**the primary endpoint**). All patients will then receive 12 months of 150 mg bid sulindac and measurements as described including MR imaging after 6 and 12 months on sulindac.

## 7.3 Primary specific aims

- a. Compare change in BD as measured by MRI-acquired fat-to-water ratio (FWR-MRI) in the *contralateral, unaffected breast pre- and post-sulindac* (primary trial endpoint).

Hypothesis: Women treated with AI + sulindac 150 mg bid will show a greater decrease in BD over 12 months when compared to their baseline change measurement.

- b. Compare pain scores using the Brief Pain Inventory-Short form (BPI-SF) *pre and post sulindac*.

Hypothesis: Women treated with AI + sulindac 150 mg bid will experience reduced pain scores over 12 months when compared to their baseline change measurement.

- c. Compare mean arterial blood pressure within individuals.

Hypothesis: Administration of 150 mg bid sulindac for 12 months to women on AIs will not lead to a clinically significant (Grade 2 or higher) increase in blood pressure when compared to their baseline change measurement.

## 7.4 Secondary Aims

- a. Compare the apparent diffusion coefficient (ADC) of water measured by diffusion-weighted MRI (DW-MRI) in the *contralateral, unaffected breast pre- and post-sulindac* (primary trial endpoint).

Hypothesis: Women treated with AI + sulindac 150 mg bid will show a significant decrease in ADC over 12 months when compared to their baseline change measurement.

## 7.5 Exploratory and Discovery Aims

- a. Correlate baseline tissue characteristics (e.g., cellularity) and tissue biomarkers (e.g., Ki67) to FWR-MRI and DW-MRI to identify tissue correlates of MR image features at baseline.
- b. Assess the association between 6-month FWR-MRI, DW-MRI, and pain scores with 12-month measures.
- c. To correlate pain scores with metabolomic measurements to determine the optimal pathways for targeting therapy designed to improve pain outcomes.
- d. Explore change in mammary gland tissue architecture, cellularity and proliferation/apoptotic index in women consenting to serial biopsy pre and post-sulindac.
- e. Assess the effect of sulindac on measures of joint stiffness and pain obtained by the Western Ontario and McMaster Universities Osteoarthritis Index (WOMAC) function, pain, and stiffness scores.
- f. Collect and bank urine for biomarker studies of NSAID effect on renal prostaglandin synthesis to relate to mean arterial blood pressure.

## 8 PARTICIPANT POPULATION

Participants will be postmenopausal women with early stage (stage 0-III) hormone receptor positive breast cancer receiving aromatase inhibitor therapy with anastrozole as part of their standard breast cancer care. There is no clinical evidence to favor selection of a particular aromatase inhibitor (anastrozole, letrozole, or exemestane). Approximately 175 participants will be recruited (100 for AI Sulindac arm and 75 for AI observation only arm). As all participants will have been adherent to AI therapy for a minimum of 3 months, we expect for AI Sulindac arm that approximately 90% will continue past the 1-month washout and 3-month observation period to intervention phase for AI Sulindac arm. We estimate an additional 10% drop-out rate prior to study conclusion (12 months imaging and patient reported outcome endpoints) for a total of 80 (Sulindac intervention) and 60 (observation only) fully evaluable participants. We have focused on women with contralateral at risk breast tissue of a BIRADS density score at least 2 ( $\geq 25\%$  BD) or scattered fibroglandular densities at least heterogenous or greater (i.e. heterogenous or mostly dense) to ensure inclusion of women with a modifiable biomarker for our primary endpoint. From our preliminary data, approximately 75% of women prescribed AIs in our clinics would meet this eligibility requirement.

## 9 INFORMATION ON STUDY AGENT FOR SULINDAC INTERVENTION

### 9.1 Sulindac

The primary target of NSAID action is either one or both of two isoenzymes, cyclooxygenase-1 (COX-1) and cyclooxygenase-2 (COX-2), involved in prostaglandin synthesis(Anderson et al. 2003). The spectrum of action of each of the individual NSAIDs and the degree that the drugs differ or overlap in target tissues remains poorly defined(Dihlmann et al. 2001). Aspirin for example has been shown to modulate not only COX-1 and COX-2 expression, but also modulates members of the  $\beta$ -catenin, EGFR and ras pathways; pathways strongly implicated in colon tumorigenesis. Similarly, COX-2 specific inhibitors show inhibitory action on the translocation of  $\beta$ -catenin to the nucleus (Williams et al. 2001). The demonstration that the COX-2 inhibitors, with lower gut related toxicity, show similar action in prevention models has driven the development of a number of highly promising COX-2 inhibition based cancer prevention trials (Arun and Goss 2004; Anderson et al. 2003). Though a strong rationale based on safety exists for the prioritization of these agents, a large body of evidence has now been accumulated that suggests that other, less target specific agents such as aspirin or sulindac may hold greater chemopreventive efficacy and perhaps anti-tumor activity due to a broader spectrum of action attributed to active metabolites (e.g., sulindac sulfone and sulindac sulfide)(Herendeen and Lindley 2003; Muir and Logan 1999) . Animal, cell culture and epidemiologic data support the concept that the observed preventive action of certain NSAID agents may be in part due to cyclooxygenase-independent activities and that certain NSAIDs, particularly sulindac, have higher potential efficacy than target specific agents such as the COX-2 specific inhibitors (Muir and Logan 1999; Karamouzis and Papavassiliou 2004).

Specifically, the anti-proliferative (cytostatic) and pro-apoptotic (cytotoxic) actions of sulindac sulfide have been attributed to p53-dependent and -independent induction of the cyclin-dependent kinase inhibitor p21waf1/cip1 with the potent pro-apoptotic activity induced by the sulfone metabolite via a COX2-independent induction of growth and differentiating factor 15 (GDF15); a member of the TGF-beta superfamily. Indeed, the potent chemopreventive activity of sulindac in models of colorectal carcinogenesis has been attributed to sulindacs ability to induce GDF15 (2). Of the NSAIDs as a class of drugs, sulindac is among the more potent inducers of GDF15. Other common NSAIDs with shorter half-lives and lower biodistribution to fatty tissues such as ibuprofen or naproxen do not induce GDF15. [name] in collaboration with [name] previously completed a randomized, open-label phase I biomarker study of sulindac to assess the effects of sulindac and its metabolites on a stable derivative of COX2-derived prostaglandins (13, 14-dihydro-15-keto prostaglandin A2 [PGEM] and the induction of GDF-15 in nipple aspirate fluid (NAF) as a surrogate of tissue bioavailability. (1). Thirty women were randomized to sulindac 150 mg qd versus sulindac 150 mg bid for a short duration of 6 weeks. Sulindac was well-tolerated in the study. Sulindac intervention was associated, in a dose-independent manner,

with a non-statistically significant decrease in NAF PGEM ( $p=0.10$ ). In this small study, GDF-15 showed was increased in NAF levels post intervention in the higher dose group of sulindac 150 mg bid ( $p=0.07$ ). These data suggested that COX2 inhibition in the breast may be achieved at 150 mg sulindac qd but that a higher dose may be needed to fully realize COX-independent benefits, such as induction of anti-apoptotic factors (e.g., GDF-15). It is partly for this reason that we chose sulindac and the 150mg BID dose for our trial.

## 9.2 Rationale for Drug Selection

The spectrum of action of each of the individual NSAIDs and the degree that the drugs differ or overlap in target tissues remains poorly defined. Sulindac and its sulfide and sulfone metabolites have been widely investigated for their COX2 dependent and independent activity as potential anti-cancer agents for multiple malignancies. Selection of sulindac over the other NSAIDs for this and our phase Ib trial (1) was based on three sulindac-specific characteristics: the lipophilic nature of the metabolites and biodistribution to breast tissue; its potent COX2 independent anti-tumor activity (not present in other NSAIDs); and the potential for lower renal toxicity and cardiovascular toxicity associated with sulindac compared to other NSAIDs.

NSAIDs as a class of drugs are associated with elevated risk of gastrointestinal (GI) toxicity among regular users. Use of proton pump inhibitors for GI symptoms has dramatically improved the use of the more potent NSAIDs such as sulindac for patients with chronic pain associated with inflammation (Hooper et al. 2004; Brown et al. 2006). In the past decade, with the completion of the coxib trials including our own ([name] et al., in preparation for JAMA), it is now clear that NSAIDs that specifically target the COX2 enzyme or the coxibs more than double the risk of cardiovascular disease (CVD), particularly in individuals with pre-existing risk factors (Marnett 2009). While data on CVD risk are more complete for coxibs, differential class-specific activity among the non-selective NSAIDs (Fosbøl et al. 2010) and the lack of safety data for the non-selective NSAIDs, including sulindac, prompted generalized warnings from the FDA regarding chronic NSAID use and risk of CVD. However, unlike other members of the NSAID class, sulindac is a prodrug with debated effects on intrarenal COX2 and limited data on endothelial cell effects. Findings for (Ciabattoni et al. 1984; Sedor et al. 1984; L.-O. Eriksson et al. 1990; Beermann et al. 1986; L. O. Eriksson et al. 1987) and against (Waslen et al. 1989; Roberts et al. 1985) renal sparing have been reported for sulindac at  $\geq 200$  mg bid in subjects with normal or mildly impaired renal function. This 'sparing' of inhibitory action on renal prostanoïd synthesis has been attributed to metabolism of sulindac to the sulfone, which exhibits no COX2 activity, in the kidney. In contrast, the inability to clear sulindac sulfide in individuals with renal insufficiency makes renal status an important consideration (Berg and Talseth 1985). As such, sulindac is

considered more renal-sparing than other traditional NSAIDs (i.e., demonstrates less pressor effects) in healthy subjects and is a drug of choice in terms of benefit-to-risk for treatment (Tx) of arthralgia in older patients. (Anthony G. Johnson 1998) In light of recent findings from the coxib trials, the effect of sulindac on blood pressure and vascular contractility is inadequately studied, especially considering the potential relevance of sulindac as a potent anti-inflammatory and anti-cancer agent. Thus, given greater anti-tumor action and pro-apoptotic activity that is unique to sulindac as a drug, the strong analgesic effects, and the recommendation of sulindac in older individuals with arthralgia, we elected sulindac for our study. With this, we also included analyses of drug effects on blood pressure endpoints in women receiving AIs for their BC treatment.

The selection of sulindac for the proposed study also allow us to study the safety of sulindac in breast cancer patients on AIs who are prone to muscle and joint pain. This increases the overall significance of the study. We have excluded women at high-risk for either cardiovascular disease or gastrointestinal toxicity from participation on the sulindac arm of the study as an additional safety precaution. These women are eligible for the observation alone arm of the study. In addition, we monitor very carefully for change in blood pressure and intervene if needed for participants who experience GI symptoms by use of PPIs or with a dose reduction.

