## **10 TOXICITY FOR SULINDAC- REPORTED ADVERSE EVENTS AND POTENTIAL RISKS**

### **10.1 Peptic ulcer and gastrointestinal bleeding**

These side effects have been reported in participants receiving Sulindac. Fatalities have occurred. Risk is higher among individuals over the age of 65. GI bleeding is associated with higher morbidity and mortality in participants with impaired by other medical conditions including hemorrhagic disorders. Combined use of NSAIDs with a proton pump inhibitor (PPI) such as omeprazole at 20 to 40 mg daily is associated with a 3-4 fold reduction in incidence of NSAID-induced gastric and duodenal ulcers, erosion, bleeding and perforation in randomized clinical trials of *Helicobacter pylori* negative patients at increased risk of ulcer (60 year and/or history of ulcer)(Lanza et al. 2009). Current guidelines recommend daily use of PPIs for gastropreservation from NSAID induced peptic ulcer and bleeding in individuals at increased risk for NSAID associated adverse GI events (e.g., 65 years or older and/or history of GI ulcer or bleeding)(Lanza et al. 2009).

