### **10.2 Serious GI toxicity**

Serious GI toxicity such as bleeding, ulceration and perforation can occur at any time with or without warning symptoms in participants treated with chronic NSAID therapy. Serious GI toxicity has been observed in approximately 1% of participants treated for 3-6 months with daily NSAIDs. Although alcoholism, smoking, history of GI disease put the participant at increased risk serious GI toxicities

have occurred in individuals with no identifiable risk factors. Elderly or debilitated participants tolerate bleeding and perforation less well than other groups and are highest risk for adverse, life threatening event. High doses of NSAIDs carry a greater risk of GI toxicity than lower dose. Daily use of PPIs significantly reduces the risk of serious GI toxicity due to erosion or ulceration including perforation in patients taking NSAIDs or COX-2 inhibitors.(Lanza et al. 2009).

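### The protocol cites guidelines for a daily PPI in higher-GI-risk NSAID users, admits women from those groups to 12 months of sulindac, and neither requires nor offers them one before symptoms

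*Protocol*

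**What the plan says.** **Cited standard.** Section 10.1 states: "Current guidelines recommend daily use of PPIs for gastropreservation from NSAID induced peptic ulcer and bleeding in individuals at increased risk". It describes the group as "individuals at increased risk for NSAID associated adverse GI events (e.g., 65 years or older and/or history of GI ulcer or bleeding". The same section says of ulcer and GI bleeding: "Risk is higher among individuals over the age of 65".

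**Risk without symptoms.** Section 10.2 says serious GI toxicity "can occur at any time with or without warning symptoms in participants treated with chronic NSAID therapy". It adds: "Serious GI toxicity has been observed in approximately 1% of participants treated for 3-6 months with daily NSAIDs". On prevention it says: "Daily use of PPIs significantly reduces the risk of serious GI toxicity due to erosion or ulceration including perforation", in patients on NSAIDs or COX-2 inhibitors.

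**Who may enter.** Section 15.2 excludes women aged 75 and over (item c), those with a GI bleed within 5 years (item i), and those with active GI symptoms despite a PPI (item j). No criterion names ulcer history. Section 15.1g requires that no contraindication to NSAIDs be known, without defining it.

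**What participants receive.** Section 21.1 gives sulindac 150 mg twice daily for 12 months. Section 9.2 is the only place that says when a participant is to be given a PPI: "intervene if needed for participants who experience GI symptoms by use of PPIs or with a dose reduction". Sections 20, 21.1, 23.1 and 24 contain no PPI rule. Section 24 deals with GI upset by dose reduction, drug holidays or stopping.

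**The concern.** The protocol sets out a preventive standard for certain NSAID users, enrols women who meet its description, and then plans a response only once symptoms appear. By its own account a symptom trigger will miss some serious events, because these can arrive unannounced. Two further statements sharpen the point. Section 24 says toxicity risk rises with use of 6 months or more, and treatment lasts 12. Section 10.2 says elderly or debilitated participants tolerate bleeding and perforation less well.

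What is at stake is participant safety, together with the meaning of the tolerability result. The SAP reports grade 3 or higher adverse events without mentioning PPI use, so a reader could not tell how many of the older women were protected. No effect on the breast density endpoint is claimed.

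**Working it through.** The plan states no figure to reproduce here; the check is mainly one of text.

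**Step 1. Groups named in 10.1 against the eligibility rules.**

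| Group in 10.1 | Rule in 15.1-15.2 | Can enter the sulindac arm? |
|---|---|---|
| Age 65 or older | 15.2c excludes 75 and over | Yes, ages 65-74 |
| Past GI bleed | 15.2i excludes the last 5 years | Yes, if more than 5 years ago |
| Past GI ulcer | Not named; 15.1g may screen out some | Possibly |

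**Step 2. What each safeguard does.**

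- *Selects:* exclusions for NSAID intolerance, recent bleed, symptoms despite a PPI, bleeding diathesis or anticoagulants, corticosteroids and current smoking; limits on outside NSAIDs and aspirin.
- *Detects:* fecal occult blood test at screening, 3-monthly visits with a focused exam, CBC (including at 6 and 12 months), telephone calls, DSMB review.
- *Reacts:* suspension at grade 2 or higher related toxicity, 50% dose reduction, drug holidays, stopping rules, and the PPI provision in 9.2.
- *Permits:* nothing forbids a preventive PPI, and a study physician signs the prescription.

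None of these gives a PPI in advance to the women in step 1.

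**Step 3. Scale, as an illustration only.** The only event rate is about 1% serious GI toxicity over 3-6 months of daily NSAIDs in general (10.2). Assume a constant rate over 12 months:

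- If the 1% refers to 6 months: 1 - 0.99^2 = 0.0199, or 2.0%.
- If the 1% refers to 3 months: 1 - 0.99^4 = 0.0394, or 3.9%.
- Per 10 women treated: 10 x 0.0199 = 0.20 to 10 x 0.0394 = 0.39 events.

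The rate in the 10.1 groups could be higher (risk rises over 65) or lower (the exclusions in step 2).

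**Step 4. What cannot be computed.** The share of sulindac starters in the 10.1 groups is not given. The 3-4 fold reduction in 10.1 comes from Helicobacter pylori "negative patients at increased risk of ulcer (60 year and/or history of ulcer" and pools ulcers, erosion, bleeding and perforation. It is therefore not applied to serious events here.

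**The case against.** The case for leaving the plan alone has real content.

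- **Participation is over.** Section 4.4 says accrual and participation are concluded, so a new treatment rule protects nobody in this trial. This stands. It limits the rule to further use of the protocol, but it does not make the plan sound.
- **A stated rationale.** Section 9.2 credits PPIs given for GI symptoms with making the more potent NSAIDs usable, and the dose of 300 mg per day is below the 400 mg maximum in section 23.1. Section 10.1 is background and sets no trial rule. This is fair, but the rationale does not address events without symptoms.
- **A PPI is not barred.** A reader might infer that a PPI may be given only after symptoms. The documents do not support that. Item 15.2j implies that women whose symptoms are controlled on a PPI can enter, so some may be covered from the first dose.
- **Not every woman with a GI history enters.** Recent bleeds are excluded, and 15.1g may remove some women with a past ulcer.
- **Section 9.2 may not contradict 15.2.** Section 9.2 says women at high GI risk were excluded; 10.1 speaks of increased risk. The protocol does not equate the two terms, so a contradiction is arguable. Section 10.2 does place elderly or debilitated participants at highest risk of life-threatening events, which makes clearer wording worthwhile.

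The guideline and the consent pages are not available to check.

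**Conclusion.** The gap is real and should be closed before this protocol is used again. Women from groups for whom the protocol itself cites daily gastroprotection can complete 12 months of sulindac without it, and the one PPI provision waits for symptoms. The finding is that prophylaxis is neither required nor offered, not that it is prohibited.

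The documents do not give the size of the benefit. The 2.0-3.9% over 12 months rests on a general NSAID rate and a constant-rate assumption, and shows scale only. A reader might infer that the rule would cut events 3-4 fold, but that figure concerns a different population and a pooled outcome. A reader might also expect the rule to rescue the SAP tolerability criterion. It would not: at the sample size of 40, the SAP can conclude that the grade 3 rate does not exceed 10% only if there are no such events, and any grade 3 event, GI or not, breaks that condition. Confidence is medium.

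**What to change.** **For any further use of the protocol**

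- Add to section 24, and list in 21.1: *Sulindac participants aged 65 or older, or with any history of GI ulcer or bleeding, take a daily PPI (e.g., omeprazole 20 mg) from first to last sulindac dose, with or without symptoms.*
- In section 20, ask for ulcer and bleed history by name.
- In section 9.2, name the GI groups that 15.2 actually excludes. This is clarification only.

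**For the present data**, beside the adverse event rates in the SAP, report:

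- the number of sulindac starters aged 65 or older;
- how many of them were on a PPI at sulindac start;
- the GI events of grade 3 or higher and the GI dropouts in that age group.

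Age and concomitant medication are already collected (sections 20 and 24). Do not compare events by PPI use: under 9.2 a PPI may be started because of symptoms, so users would look worse through confounding by indication.

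**Cost.** One treatment rule, one screening question, one wording change and a short descriptive entry in the safety report. The downsides are pill burden, expense, and a tolerability result that applies to sulindac plus a PPI in these women.
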